17.3. Privacy and Confidentiality

A participant's privacy and confidentiality will be respected throughout the study. Each participant will be assigned a unique identification number and these numbers rather than names will be used to collect, store, and report participant information. Site personnel will not transmit documents containing protected health information (PHI) to the study sponsor or their representatives.

18. Additional Regulatory Items

18.1. Transfer of Study Materials and Data

Some samples that are collected during research activities may be frozen and shipped to other hospitals, institutions, and testing companies for analysis. Data may also be shared. The data and/or samples will be de-identified per the Health Insurance Portability and Accountability Act (HIPAA) and have no protected health information (PHI) associated with them. The data and/or samples will be used in a collaborative relationship between institutions, or testing companies receiving the data and/or samples. All of these samples will be shared under a Material Transfer Agreement (MTA), or other applicable agreement.

18.2. Closure of Study Sites

If the PI in coordination with DAIT/NIH chooses to close out the study site (for example, due to lack of participant enrollment within a reasonable period of time, violation of the study agreement, breach of protocol, early attainment of study enrollment targets, etc.), the PI will notify involved individuals in writing. The appropriate regulatory agencies must be informed according to applicable requirements, and adequate consideration must be given to the protection of the participants' interests.

18.3. Archiving of study documents

All essential study documents must be retained by the investigator for at least 3 years after the conclusion or discontinuation of the trial. Prior to destroying any essential documents, the investigator must consult with the study sponsor ([name], PhD). If, and when, destruction is authorized, records must be destroyed in a manner that ensures confidentiality. If an investigator can no longer ensure archiving, the sponsor and the investigator will agree upon a suitable designation for transferring the essential records.

Appendix 1.0

Anaphylaxis

Clinical criteria for diagnosing anaphylaxis will be as follows ²⁷:

Anaphylaxis is highly likely when any one of the following 3 criteria is fulfilled:

1. Acute onset of an illness (minutes to several hours) with involvement of the skin, mucosal tissue, or both (e.g., generalized hives, pruritus or flushing, swollen lips-tongue-uvula)

AND AT LEAST ONE OF THE FOLLOWING:

 - a. Respiratory compromise (e.g., dyspnea, wheeze-bronchospasm, stridor, reduced Peak expiratory flow (PEF), hypoxemia)
 - b. Reduced blood pressure (BP) or associated symptoms of end-organ dysfunction (e.g., hypotonia [collapse], syncope, incontinence)
2. Two or more of the following that occur rapidly after exposure to a likely allergen for that patient (minutes to several hours):
 - a. Involvement of the skin-mucosal tissue (e.g., generalized hives, itch-flush, swollen lips-tongue-uvula)
 - b. Respiratory compromise (e.g., dyspnea, wheeze-bronchospasm, stridor, reduced PEF, hypoxemia)
 - c. Reduced BP or associated symptoms (e.g., hypotonia [collapse], syncope, incontinence)
 - d. Persistent gastrointestinal symptoms (e.g., crampy abdominal pain, vomiting)
3. Reduced BP after exposure to known allergen for that patient (minutes to several hours):
 - a. Systolic BP of less than 90 mm Hg or greater than 30% decrease from that person's baseline

*Low Systolic BP is defined as less than $(70 + [2 \times \text{age}])$ mm Hg

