4.2. Inclusion Criteria for Double Blind Phase

Individuals who meet all of the following criteria are eligible for enrollment as study participants:

1. Participant and/or parent guardian must be able to understand and provide informed consent and/or assent prior to the study procedures being performed.
2. Willing and able to comply with study visits and activities.
3. Age ≥ 12 and < 71 years at study enrollment.
4. Histologically active EG at time of screening, with a peak gastric count of ≥ 30 eos/hpf in at least 5 hpf in the gastric antrum and/or body with no other known cause for gastric eosinophilia; involvement of eosinophilic inflammation in other gastrointestinal segments will be allowed but not required or sufficient.
5. History (by patient report) of moderate to severe EG symptoms (stomach pain, stomach cramping, nausea, bloating, burning feeling in the chest, starting to eat and feeling full too quickly, loss of appetite, vomiting, or diarrhea) at least 2 days per week in the 2 weeks prior to screening.
6. EG symptoms (stomach pain, stomach cramping, nausea, bloating, burning feeling in the chest, starting to eat and feeling full too quickly, loss of appetite, diarrhea, or vomiting) at least 2 days per week in the two weeks leading up to V1 (randomization) documented via EG-SQ eDiary. At least 8 of 14 days must be entered in the EG-SQ eDiary in the 2 weeks prior to V1 (randomization).
7. Stable medical management of EG (and other eosinophilic disorders, if applicable) including stable dosage of medications in the 8 weeks prior to study enrollment. Participants may be on baseline anti-EG therapy (such as elimination diet, elemental diet, proton pump inhibitors, topical swallowed or systemic glucocorticoids (≤ 10 mg daily), immunosuppressive agents, cromolyn, and H1 and H2

anti-histamines) as long as there is agreement not to change their dosage unless medically indicated. See section 7.1 Concomitant and other Treatments for additional details.

8. Willing to maintain current dietary regimen throughout the course of the study. Diet must have been stable for 8 weeks prior to baseline endoscopy.
9. If have asthma and/or any other chronic allergic conditions (e.g., chronic rhinosinusitis with nasal polyposis), they must be willing to maintain their pretrial medications until the end of study. Medication dose can be increased if there is a deterioration in the condition.
10. Score on Asthma Control Test (ACTTM) ≥ 20

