4.4. Exclusion Criteria for Open Label Extension

A participant who meets any of the following criteria will not be permitted to enter the Open Label Extension portion of the study:

- 1. Participants who, during the double-blind treatment period, developed a serious adverse event (SAE) deemed related to study drug
- 2. Participants who, during the double-blind treatment period, developed an adverse event (AE) deemed related to study drug which in the opinion of the investigator could indicate that continued treatment with the study drug may present an unreasonable risk for the patient
- 3. Participants who, during the double-blind treatment period, were prematurely withdrawn because of a protocol violation, poor compliance or inability to complete required study assessments.
- 4. Participants who became pregnant during the double-blind treatment period.
- 5. Participants who are prematurely discontinued from study drug due to an AE. Participants who are prematurely discontinued from study drug, but not withdrawn from the study, due to lack of efficacy are eligible to enter the OLE.

6. Participants who did not undergo endoscopy with biopsies at the EOT (visit 5).
7. Systemic hypersensitivity to dupilumab or the excipients of the drug product based on participation in the double-blind phase of the trial.
8. Participants who are unable or unwilling to administer home doses of dupilumab during open label

5. Known and Potential Risks and Benefits to Participants

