6.5. Premature Discontinuation of Investigational Agent

Study therapy will be prematurely discontinued for any participant for any of the following reasons:

- Evidence of pregnancy.
- Suspected diagnosis of serum sickness related to the study drug (constellation of signs and symptoms that include arthritis/arthralgia, rash, fever, and lymphadenopathy).
- Clinical features of vasculitis.
- An infection that:
 - Requires parenteral treatment with an antibiotic, antifungal, antiviral, anti-parasitic, or antiprotozoal agent
 - Requires oral treatment with such agents for longer than 2 weeks
 - Is opportunistic, such as tuberculosis and other infections whose nature or course may suggest an immune-compromised status
- Anaphylaxis possibly related or related to investigational product according to the Sampson criteria (Appendix 1).
- A grade 3 injection site reaction.
- Evidence of non-compliance to study protocol such as missing more than one dose of study drug.
- The investigator feels that continuing use of the investigational product no longer in the best interest of the participant.
- Grade 3 or higher adverse event based on CTCAE 5.0 grading that is possibly related/related to the investigational product
- Grade 4 or higher adverse event based on AEC grading (Section 12.3.1, Table B) that is possibly related/related to the investigational product

7. Other Medications

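### The Appendix 1 footnote sets low systolic BP at 70 + 2 × age mm Hg with no age range, which conflicts with criterion 3a's 90 mm Hg at every eligible age

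*Protocol*

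**What the plan says.** Protocol Appendix 1.0 lists three criteria, any one of which makes anaphylaxis highly likely. Blood pressure enters all three.

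- Criterion 1b: "Reduced blood pressure (BP) or associated symptoms of end-organ dysfunction", alongside acute skin or mucosal involvement. No figure is given.
- Criterion 2c: reduced BP again, as one of four features of which two are needed. No figure is given.
- Criterion 3a, after exposure to an allergen known for that patient: "Systolic BP of less than 90 mm Hg or greater than 30% decrease from" the person's baseline.

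Beneath these, an asterisked footnote states "Low Systolic BP is defined as less than" 70 + 2 × age mm Hg, with no age range. In the text available for this review no criterion carries a matching asterisk. It may have been lost when the PDF was converted, and the point does not depend on it.

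Inclusion criterion 3 (section 4.2) is "Age ≥ 12 and < 71 years at study enrollment".

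The appendix is put to use in two places. Section 6.5 opens "Study therapy will be prematurely discontinued for any participant for any of the following reasons" and lists anaphylaxis under Appendix 1 when it is judged possibly related or related to the investigational product. Section 11.1.1, item 12, makes the same event a ground on which a participant may be terminated from the study. Section 4.4, item 5, then keeps out of the open-label extension (OLE) "Participants who are prematurely discontinued from study drug due to an AE".

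**The concern.** The definition contains two numeric limits for the same measurement, and they agree for nobody in the trial. The footnote's limit rises by 2 mm Hg per year of age, so from the mid-twenties it labels ordinary systolic pressures as low.

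Sites take vital signs after supervised injections (Schedule of Activities, Table A). Criteria 1b and 2c give no figure, so a site looking for one finds two on the page. If the footnote's figure is used in 1b, an acute skin reaction with ordinary blood pressure counts as anaphylaxis. In 2c, ordinary blood pressure supplies one of the two features required.

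Once such an event is judged possibly related or related, section 6.5 requires study drug to stop. If this happens in the double-blind phase, entry to the OLE is barred.

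**Working it through.** The plan states a formula and no derived value, so there is no reported figure to reproduce. The check is to evaluate the formula over the eligible ages and compare it with criterion 3a.

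**Inputs.** Footnote limit: 70 + 2 × age (Appendix 1.0). Criterion 3a: below 90 mm Hg, or a fall of more than 30% from baseline (Appendix 1.0). Ages: 12 to under 71 (section 4.2, item 3), which is 70 − 12 + 1 = 59 whole-year ages.

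**Where the limits meet.** 70 + 2 × age = 90 gives age = (90 − 70)/2 = 10. That is below the minimum eligible age, and the formula only rises from there.

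**Values at eligible ages.**

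| Age | 70 + 2 × age (mm Hg) | Excess over 90 |
|---|---|---|
| 12 | 94 | 4 |
| 18 | 106 | 16 |
| 40 | 150 | 60 |
| 70 | 210 | 120 |

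The footnote exceeds 90 at all 59 ages. Section 13.1 describes participants as 18 to 70. On that range the limit runs from 106 to 210 and the conclusion is the same.

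**Two ordinary readings, if the footnote is applied.**

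- Systolic 100 is low when 70 + 2 × age > 100, so age > 15. That is ages 16 to 70, or 55 of 59. Under 3a it counts only if baseline exceeded 100/0.7 = 142.9 mm Hg.
- Systolic 120 is low when 70 + 2 × age > 120, so age > 25. That is ages 26 to 70, or 45 of 59. Under 3a it counts only if baseline exceeded 120/0.7 = 171.4 mm Hg.

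**The other direction, if the footnote is read as replacing 3a.** The 30% limb then disappears. Take age 12, baseline 140, reading 96. The fall is (140 − 96)/140 = 31.4%, which meets 3a, but 96 is not below 94, so the footnote does not count it. For a case to be lost this way the reading must be at or above the footnote limit and below 0.7 × baseline, so baseline must exceed limit/0.7:

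- age 12: 94/0.7 = 134.3 mm Hg
- age 18: 106/0.7 = 151.4 mm Hg
- age 40: 150/0.7 = 214.3 mm Hg

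The possibility is therefore largely confined to young participants with a raised baseline.

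**The case against.** The strongest reply is that the footnote governs nothing. It has no visible anchor, it says 'Low' where the criteria say 'Reduced', and it is not itself one of the three criteria that sections 6.5 and 11.1.1 invoke. Its natural home is criterion 3a, which has its own figure and needs an allergen already known for that patient. Prior dupilumab exposure and prior anaphylaxis to a biologic are both exclusions (section 4.3, items 11 and 12), so study drug will seldom be a known allergen, at least at first dosing. A clinician would also see that calling 120 mm Hg low at age 26, or 200 at age 70, makes no sense. All of this stands, and it is why the likely effect is small. It does not make the figure right for any participant.

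Existing rules also overlap with the consequence. The investigator may already stop drug in the participant's interest, and related events of Grade 3 or higher already stop it (section 6.5). OLE exclusions 2 and 7 cover unreasonable-risk events and systemic hypersensitivity. Final attribution for safety reporting rests with the sponsor after consultation (section 12.3.2). What remains is mainly milder related reactions without a true fall in pressure.

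Timing limits it further. SAP version 2.4 (February 2025) already refers to double-blind results, so the OLE-entry consequence may be past. The SAP reports one double-blind dropout, on placebo. That is not a count of drug discontinuations, but it gives no sign of widespread over-calling.

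A reader might go further than the documents allow in three ways:

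- That normal blood pressure now counts as anaphylaxis in this trial. Nothing ties the footnote to 1b or 2c, and both need other features as well.
- That the error is safe because it can only over-call. This holds only if the footnote adds to 3a. Read as a replacement, it can miss a case.
- That efficacy results or the enrolment halt are affected. Section 11.4 is triggered by death, CTCAE grade and eosinophil-count grade, and does not refer to Appendix 1. The intent-to-treat set keeps everyone who received a dose (section 11.2).

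**Conclusion.** The footnote is wrong as written for this population. It conflicts with criterion 3a at all 59 eligible whole-year ages, by 4 mm Hg at age 12 and 120 mm Hg at age 70, inside a definition used for mandatory drug discontinuation and possible withdrawal. The arithmetic is certain and needs no assumption beyond the printed formula and the age criterion.

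The consequence is less certain, because it depends on how a site reads an unanchored line. Carried into 1b or 2c it over-calls anaphylaxis; substituted for 3a it can also miss a case. The documents show neither happening and give no basis for estimating how many participants could be affected. Severity is minor, with no effect on the efficacy analysis.

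**What to change.** Delete the footnote, leaving criterion 3a as the only numeric blood-pressure limit in Appendix 1.0. Restricting it to ages 10 and below would also remove the conflict, but age 10 is only where the two numbers cross. No document supports it as a clinical range, and it would cover no eligible participant, so deletion is cleaner. Whether 1b and 2c should borrow 3a's figures is for the sponsor's medical lead.

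This is one line in the next routine amendment, with the approvals in section 18.4 (sponsor, CCHMC, central IRB, NIAID). Visits, procedures and data collection do not change.

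The documents do not say whether OLE dosing has finished. If it has, the equivalent step is to check, before the adverse event summaries are final, that no event was classified as anaphylaxis, or ruled out, on the strength of the footnote.

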## SAP Revision History

| Version | Date      | Changes   |
|---------|-----------|---|
| 1.0     | 9/19/2023 | Development of initial SAP  |
| 2.0     | 6/18/2024 | 
 
1. Placing SAP on standardized template
 
2. Adding variable definitions for derived variables.
 
3. Changing EGID abbreviations to updated standard
 
  |
| 2.1     | 7/17/2024 | Added hierarchical testing structure for key secondary outcomes   |
| 2.2     | 8/1/2024  | Changed the rules for the window around the symptom diary reporting for EOT. Using time since baseline may have impact on missing rate.   |
| 2.3     | 12/5/2024 | Change to remove internal inconsistency. When hierarchical testing structure was added EoG HSS was not moved from an exploratory outcome to a key secondary outcome. Based on findings from the clinical trial of benralizumab in EoG, the study team agreed that EoG HSS was a key secondary outcome. When the study was initially designed, EoG HSS had not been evaluated clinically, thus it was not placed as a key secondary outcome. |
| 2.4     | 2/12/2025 | Changed the analysis population for the key primary and secondary outcomes to the complete case ITT due to similarity of results using imputed data and limited missingness.  |

## List of Abbreviations

|           |   |
|-----------|---|
| ACT       | Asthma Control Test   |
| AE        | Adverse Event   |
| AEC       | Absolute Eosinophil Count   |
| BP        | Blood Pressure  |
| CBC       | Complete Blood Count  |
| CCHMC     | Cincinnati Children's Hospital Medical Center   |
| CEGIR     | Consortium of Eosinophilic Gastrointestinal Disease Researchers                       |
| CFR       | Code of Federal Regulations   |
| CGI-C     | Clinician Global Impression of Change   |
| CGI-S     | Clinician Global Impression of Severity   |
| CRF       | Case Report Form  |
| COVID     | Coronavirus Disease   |
| CTCAE     | Common Terminology Criteria for Adverse Events  |
| DAIT      | Division of Allergy, Immunology, and Transplantation                                  |
| DBP       | Double Blind Phase  |
| DEGAS     | Dupilumab Eosinophilic Gastritis Study  |
| DNA       | Deoxyribonucleic Acid   |
| DSMB      | Data Safety Monitoring Board  |
| EoD       | Eosinophilic Duodenitis   |
| EoE       | Eosinophilic Esophagitis  |
| EoG       | Eosinophilic Gastritis  |
| EGD       | Esophagogastroduodenoscopy  |
| EGID      | Eosinophilic Gastrointestinal Disorder  |
| EoG-EREFS | Eosinophilic Gastritis Endoscopy Assessment   |
| EoG-SQ    | Eosinophilic Gastritis Symptom Questionnaire  |
| EOS       | End of Study (Completion of telephone contact 12-weeks after last dose of study drug) |
| EOT       | End of Treatment  |
| EREFS     | Endoscopic Reference Score  |
| FDA       | Food and Drug Administration  |
| GCP       | Good Clinical Practice  |
| hpf       | High Power Field  |
| HSS       | Histology Scoring System  |
| ICF       | Informed Consent Form   |
| ICH       | International Conference on Harmonization   |
| IgE       | Immunoglobulin E  |
| IL        | Interleukin   |
| IND       | Investigational New Drug  |
| IPM       | Independent Protocol Monitor  |
| IRB       | Institutional Review Board  |
| IP        | Investigational Product   |
| ITT       | Intention to Treat  |
| mAb       | Monoclonal Antibody   |
| MCAR      | Missing at Completely Random  |
| MO        | Medical Officer   |
| MOP       | Manual of Procedures  |
| NIAID     | National Institute of Allergy and Infectious Diseases                                 |
| OLE       | Open Label Extension  |
| PP        | Per Protocol  |
| PGI-C     | Patient Global Impression of Change   |
| PGI-S     | Patient Global Impression of Severity   |

|        |  |
|--------|--|
| PHI    | Protected Health Information                             |
| PI     | [Site] Principal Investigator                            |
| PM     | Project Manager  |
| PoR    | Pharmacist of Record                                     |
| PRO    | Patient Reported Outcome                                 |
| PROMIS | Patient Reported Outcomes Measurement Information System |
| QC     | Quality Control  |
| QOL    | Quality of Life  |
| RDCRN  | Rare Diseases Clinical Research Network                  |
| RNA    | Ribonucleic Acid   |
| SAE    | Serious Adverse Event                                    |
| SAP    | Statistical Analysis Plan                                |
| SAR    | Suspected Adverse Reaction                               |
| SC     | Subcutaneous   |
| SF-12  | Short Form 12 Health Survey                              |
| SOA    | Schedule of Activities                                   |
| SODA   | Severity of Dyspepsia Assessment                         |
| SOP    | Standard Operating Procedure                             |
| SUSAR  | Serious Unexpected Suspected Adverse Reaction            |
| TEAE   | Treatment-Emergent Adverse Event                         |
| Th2    | Type 2 Helper  |

## Introduction

The primary objective of this study is to assess the efficacy and safety of Dupilumab in the treatment of Eosinophilic Gastritis. This document outlines the statistical methods to be implemented during the analyses of data collected within the scope of Consortium of Eosinophilic Gastrointestinal Disease Researchers' Protocol CEIGR 7810 titled "A Randomized, double-blind, placebo-controlled clinical trial to evaluate the efficacy of dupilumab (anti-IL4ra) in subjects with eosinophilic gastritis". This Statistical Analysis Plan (SAP) was prepared in accordance with CEGIR 7810 protocol, V6.0, dated 12/6/2023.

The purpose of this Statistical Analysis Plan (SAP) is to provide a framework in which answers to the protocol objectives may be achieved in a statistically rigorous fashion, without bias or analytical deficiencies, following methods identified prior to database lock. Specifically, this plan has the following purposes:

- To prospectively outline the specific types of analyses and presentations of data that will form the basis for conclusions.
- To explain in detail how the data will be handled and analyzed, adhering to commonly accepted standards and practices of biostatistical analysis. Any deviations from these guidelines must be substantiated by sound statistical reasoning and documented in writing in the final clinical study report (CSR) or manuscript.

The analyses described in this analysis plan are consistent with the analyses described in the study protocol. The order may be changed for clarity. If there are discrepancies between the protocol and SAP, the SAP will serve as the definitive analysis plan.

Any analysis performed not prospectively defined in this document will be labeled as post hoc & exploratory.

